6.2.1. Secondary and Exploratory Efficacy Endpoint Analysis

For viral loads of RSV-A Memphis 37b as determined by quantitative RT-PCR assay and by quantitative culture of RSV, number of observations, mean, standard error, median, first and third interquartile will be tabulated and means with standard errors will also be graphically presented per time point.

For clinical symptoms scores, total clinical symptom scores, mucus weight and number of tissues, number of observations, mean, standard error, median, first and third interquartile will be tabulated and means with standard errors will also be graphically presented per time point.

For peak viral load based on the quantitative RT-PCR assay, number of observations, mean, standard error, median, first and third interquartile will be tabulated for both groups and graphically presented with boxplots. Exact Wilcoxon Rank Sum tests will also be performed to compare the mean in the active versus placebo groups and the corresponding p-values will be presented. Note the study is only powered for the primary efficacy endpoint and not for any of the secondary one, interpreting these p-values should be done with caution.

For AUCs of viral loads, clinical symptoms and mucus weight, number of observations, mean, median, first and third interquartile (q1, q3) will be calculated for both groups and graphically presented with boxplots. Exact Wilcoxon Rank Sum tests will also be performed to compare AUCs in the active versus placebo groups and the corresponding p-values will be presented. Note the study is only powered for the primary efficacy endpoint and not for any of the secondary one, interpreting these p-values should be done with caution.

Descriptive statistics (number of observations, mean, standard errors, median, q1, q3) of values and changes from baseline for FEV₁, FVC, and FEV₁/FVC will be summarized at each scheduled timepoint. Mean with standard errors of actual values and changes from baseline will also be graphically presented. Finally, spirometry values that are below the clinically important limits, provided in the table below, will be classified as ‘abnormally low’ and the percentage of subjects with ‘abnormally low’ values will be summarized.

Parameter	Clinically Important Limits
FEV ₁	80%
FVC	80%
FEV ₁ /FVC	70%

The proportion of subjects with symptomatic RSV infection per group for each one of the three with symptomatic RSV infection definitions, Conservative, Liberal (RT-PCR), Liberal (RT-PCR or Serology), will be tabulated and presented graphically with bar charts. Moreover, the difference in proportions and corresponding confidence intervals (CIs) will be calculated, if available. These will also be presented graphically with a forest plot.

The relation between viral load and clinical symptoms will be graphically explored. Moreover, summary statistics of efficacy endpoints might be repeated, for the infected and for the not infected subjects based on the three symptomatic RSV infection definitions.

Finally, subject specific profiles of viral loads total clinical symptom scores, mucus weight and tissue count will be created.

7. SAFETY

Safety analyses will be performed on the FA. Continuous variables will be summarized using the following statistics, as appropriate: number of observations, median, quartiles (Q1 and Q3), minimum and maximum. Frequencies and percentages (one decimal place) will be generated for categorical variables. No formal comparisons between groups will be provided.

One type of safety tables will be shown. The by regimen layout, safety data will be analyzed by vaccine regimens as designed per protocol; data will be presented by period. Denominator for the percentages is the number of subjects in the considered population and period for a certain regimen (incidence per 100 subjects/phase).

7.1. Adverse Events (AE)

7.1.1. Definitions

Solicited AEs, collected for 7 days after vaccination, shown in the tables are extracted from the diary pages of the CRF. For unsolicited AEs, only AEs with start date (grade and/or relation) within the 28-day period following vaccination or challenge will be presented in the safety tables except for SAE, which will be captured and tabulated in the outputs covering the whole study period. All other collected unsolicited adverse events will be presented through listings.

Solicited local AEs will be by definition considered as related to the study vaccine.

The severity of the AEs will be classified as grade 1 to 4. Solicited events that are graded less than grade 1, are not considered as AE. In case no grades are available, the grading of the solicited events will occur according to the grading list in [Attachment 1](#).

7.1.2. Analysis of Adverse Events

Number and percentage of subjects with at least one particular AE (unsolicited/solicited) will be tabulated. Unsolicited AEs will be summarized by System Organ Class and Preferred Term. Solicited AEs will be summarized by class (local, systemic) and preferred term.

For solicited AEs following tables will be provided: summary, by worst severity grade, grade 3, related (systemic only), time to onset (in days) and duration (in days) for most frequent events and body temperature. Note: For solicited events, duration is defined as number of days from the start of the event until resolution of the event. The time to first onset is defined as (date of first onset – reference date + 1). The reference date is the start date of the regimen period.

For unsolicited AEs following tables will be provided: summary table (including SAE, fatal outcome, AESI and discontinuation), all events, most frequent, grade 3, permanent stop of vaccine, related, SAE.

Listings and/or subject narratives will be provided as appropriate, for those subjects who die, discontinue study vaccinations due to an AE, or experience a severe or serious AE.

7.1.3. Phase allocation of Adverse Events

Solicited events are always allocated to the Post Dose period.

Solicited AEs from the diary will be added to the ADAM for unsolicited AEs according to the same principles. This means the same event occurring on different days will be allocated to one row with the start date of the AE being the first date of the event and the end date for the event is the last subsequent day of the event. A change in grade will trigger a new row to be added. The same occurs in case of non-subsequent events (for example grade 1 nausea on day 1, 2 and 3 and also on day 6 and 7, which will be allocated to two rows; the duration of the event is 7 days). For further details related to transforming the on-site assessments and diaries of solicited AEs into analysis format please refer to [Attachment 2](#).

Step 1: Allocation of events to the periods:

Adverse events in the SDTM database are allocated to periods based on their start date/time. If the start date/time of an event falls between (or on) the start and stop date/time of a period, the AE is attributed to that period (treatment-emergent principle).

- In case of partial start or stop dates (i.e. time and/or day and/or month and/or year missing), the events are allocated to the periods using the available partial information on start and end date; no imputation will be done. If, for instance, the AE start date only month and year are available, these data are compared to the month and year information of the periods. This rule may lead to multiplication of the event as a consequence of its assignment to multiple periods.
- In case of a completely missing start date, the event is allocated to the first active treatment phase (post dose period), except if the end date of the AE falls before the start of the first active treatment phase (post dose period).
- In case of a completely missing end date, the date is imputed by the cut-off date of the analysis for subjects still ongoing in the study, and by the end date of the last period for subjects who discontinued or completed the trial.

Step 2: Combination of events:

Overlapping/consecutive events are defined as events of the same subject with the same preferred term which have at least 1 day overlap or for which the start date of an event is 1 day after the end date of the preceding event. Overlapping/consecutive events may be combined into one AE or not, according to the following rules:

1) If overlapping/consecutive events start in one of the following periods - Screening or follow up (i.e. non-active periods) - followed by an AE in - post-dose or challenge period (active period) - they are allocated to their respective periods and are considered as separate events.

2) In case overlapping/consecutive events start within a single period, they are considered as one and the same AE. The individual events which contribute to this AE are retained as individual records in the ADaM database but are assigned the same onset, period, and total duration. All related attributes to the AE/phase/period should also be consistent with the new event.

3) In case overlapping/consecutive events start in both an active period followed by a non active period, they are allocated to the active period only and are considered as one and the same AE. The individual events which contribute to this AE are retained as individual records in the ADaM database but are assigned the same onset, treatment period, and total duration. All related attributes to the AE/phase/period should also be consistent with the new event.

4) In case an active period is followed by another active period, and the overlapping/consecutive events start in both periods, they are allocated to their respective period and are considered as separate AEs. The same rule applies for 2 non-active periods.

Remarks:

1. Events can only be combined into one and the same AE if their start and stop dates are known.
2. In case the completely missing end date is imputed (for period allocation), this date is also considered as a complete date.
3. Time is not considered when determining overlap of events.

7.1.4. Missing Data

Missing data will not be imputed. Subjects who do not report an event will be considered as subjects without an event. The analysis of the solicited AEs will include only documented safety data.

7.1.5. Solicited Local (Injection Site) Reactions

The analysis of local solicited adverse events, for all subjects after vaccination will include:

- Erythema
- Induration/swelling
- Pain/tenderness

7.1.6. Solicited Systemic Adverse Events

The analysis of systemic solicited adverse events for adult subjects after vaccination will include:

- Fatigue
- Headache

- Myalgia
- Arthralgia
- Chills
- Nausea
- Fever (ie, body temperature ≥ 38 °C)

7.2. Clinical Laboratory Tests

For laboratory safety parameters, only abnormalities emerging will be tabulated by worst abnormality grade using the FDA table in [Attachment 1](#). Blood and urine for laboratory safety assessments will be collected within 56 days of vaccination, pre-vaccination, at 7 days post vaccination, prior to challenge on Day -1 or Day -2, post challenge at day 12 and Day 28. Moreover, blood for assessment of cardiac enzymes will also be collected on Days 3, 7, and 11.

An abnormality (toxicity grade or abnormality based on normal ranges) will be considered as emerging in a particular period if it is worse than the baseline value. If the baseline is missing, the abnormality is always considered emerging. A shift from ‘abnormally low’ at baseline to ‘abnormally high’ post baseline (or vice versa) is also emerging. In case a laboratory test result is censored (no numeric value is available, but only a verbatim term) then a numeric value will be imputed by a value exceeding the cut-off value with one unit. (<x: subtract 1 unit from x, >x: add 1 unit to x; <3.45 is imputed with 3.44).

In case no toxicity grades are defined for a test, the abnormalities (above/below normal range) will be used. In determining toxicity grades, the following rules are applied:

- worst grades/abnormalities are determined over the whole observational period for each trial period separately, including all post-baseline measurements of that period.
- The abnormalities ‘abnormally low’ and ‘abnormally high’ are considered equally important, i.e. if a subject has as well an abnormally low as an abnormally high value post-baseline, both abnormalities are shown in the tables. (This means that the sum of the percentages can be more than 100%)
- Note: as the grading scale for some parameters in the grading table has some gaps (zones where no toxicity grade definition exists), laboratory results falling in these zones will be allocated to the adjacent worst-case grade.
- If a laboratory value falls within the grading as specified in the grading table but also within the local lab normal limits, the value is considered as normal.
- HGB: for hemoglobin grades are based on both actual values and changes. Those grading will be listed separately. In addition, for the grading on the changes of HGB, the corresponding actual value should be at least grade 1.

- Only the lab values are used in determining the toxicity grades. For some lab parameters, extra clinical assessments are available to attribute grade 4 toxicity (eg. requiring hospitalization or dialysis), but these are not taken into account in the lab analysis

For the grades, no distinction will be made between test results of samples obtained under fasting and under non-fasting conditions: in case limits under fasting and non-fasting conditions differ, the limits of the conditions (fasting/non-fasting) of scheduled visits as planned in the CTP will always be used, also for samples obtained under a different condition (e.g. samples of withdrawal visits).

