Blood will be collected for sero-susceptibility (neutralizing antibody to RSV-A Memphis 37b) within 90 days of vaccination and on entry to the Unit. Blood and urine will be collected for laboratory safety assessments within 56 days of vaccination, pre-vaccination, at 7 days post-vaccination and prior to challenge on Day -1 or Day -2. Blood will additionally be collected for biochemistry and hematology assessments at discharge from the quarantine Unit and at 28 days post-challenge. Blood for assessment of cardiac enzymes will also be collected on Days 3, 7, and 11.

Blood samples for humoral and cellular immunity will be collected pre-vaccination, 1-2 days prior to challenge, and at 28 days after challenge. *Note:* blood samples for immunogenicity

[figure not shown]
assessment will be collected from all subjects whether subjects are challenged or not (ie, including “overflow” subjects). Blood draws for overflow subjects who are not challenged will occur at 28 days post-vaccination and again 28 days later. Overflow subjects who are challenged in a later cohort will also have blood draws at the time of challenge and 28 days after challenge.

RSV pre-F antibody will be assessed on the day before challenge and at discharge from the Unit from nasal wash samples.

An internal data review committee (DRC) will be commissioned for this study, the members of which consist of a clinician with expertise in vaccines and infectious diseases, a medical safety officer and a statistician, none of whom will be part of the study team or involved in the conduct of the study. The DRC will meet if, in the judgment of the investigator and/or the sponsor’s SRP, a significant or unexpected safety event occurs.

The end of the study will be the last subject’s last visit by telephone at 6 months after vaccination.

A diagram of the study design is provided in [Figure 1](#).

Figure 1: Schematic Overview of the Study

* Historical pre-screening data collected through the ethics committee-approved hVIVO screening protocol within 56 days to 3 days prior to vaccination (90 days for viral serology) may be used for screening procedures. Historical pre-screening data obtained prior to this window can be re-assessed any time from 40 days to 3 days prior to vaccination.

RVAT = rapid virus antigen test

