9.1.6. Day 28 Post-challenge

The visit at 28 days post-challenge will include an abbreviated physical examination (at the discretion of the investigator), and vital signs measurement. Blood samples for immunogenicity assessments will be collected. Any unsolicited AEs/SAEs and concomitant medications will be recorded, and blood samples collected for clinical laboratory tests (hematology and biochemistry only). A urine pregnancy test will be performed for all female subjects.

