9.2.6.2. Clinical Laboratory Tests

Blood and urine samples for laboratory safety assessments will be collected for screening up to 56 days prior to vaccination, pre-vaccination, 7 days post-vaccination, and prior to challenge on Day -1 or Day -2. Blood samples will additionally be collected at discharge from the quarantine Unit and at 28 days post-challenge. The following tests will be performed by a local laboratory (*parameters only measured at screening):

- **Hematology Panel**

- platelet count.
- white blood cell (WBC) count (absolute)
- WBC differential
 - neutrophils
 - lymphocyte
 - monocytes
 - eosinophils
 - basophils
- red blood cell (RBC) count
- reticulocyte count (% and absolute)
- hemoglobin
- hematocrit
- mean corpuscular volume (MCV)
- mean corpuscular hemoglobin (MCH)
- MCH concentration (MCHC)

- **Biochemistry Panel**

- sodium
- potassium
- glucose (random)
- albumin

chloride
bicarbonate
calcium
uric acid
total protein
creatinine
total, direct, and indirect bilirubin
inorganic phosphate
blood urea nitrogen
C-reactive protein
gamma glutamyl transferase
alkaline phosphatase
alanine transaminase
lactate dehydrogenase
aspartate transaminase
urea

- **Cardiac Enzymes** (done together with ECGs on admission, and on Days 3, 7 and 11)

Troponin T
creatinine kinase

- **Urinalysis** – dipstick for:

specific gravity
pH
glucose
protein
blood
ketones
appearance
color
nitrite
urobilinogen
bilirubin
leucocytes

A repeat urinalysis will be performed in the event of a positive dipstick test. Microscopic reflex testing will be carried out if the repeat urinalysis dipstick test is also positive.

Review and Grading of Laboratory Data

The investigator must review each laboratory result, document this review and assess systematically any clinical significance. The laboratory reports must be filed with the source documents.

Laboratory values will be initially evaluated by the investigator according to local laboratory criteria. Abnormal values outside the local laboratory range of normal will be graded according to the FDA Guidance document “Toxicity Grading Scale from Healthy Adult and Adolescent Volunteers Enrolled in Preventive Vaccine Clinical Trials” (see [Attachment 1](#)). Laboratory values within local laboratory normal limits will not be FDA graded and will be considered as normal.

Reporting Laboratory Abnormalities as AEs

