- worst emergent abnormalities: HR, PR, QRS, QTc, QTc change

Percentages will be calculated relative to the total number of subjects with data.

Note: RR values will only be listed, as well as any original QTc parameter, if provided in the DB. Recalculated HR values will be flagged.

In Case of Missing Date or Time Parts

ECG records with missing assessment date- or time-parts (any: day, month or year) will not be used for descriptive statistics, unless the scheduled target day or time is known and a unique study day allocation is possible taking this additional information into account. These assessments will be allocated to the right study day using the available date (time) information, and the information on their assessment schedule. In case it is not possible to assign a study day to those measurements they will only appear in a listing, including a flag.

Emergent Definition for Abnormalities

Abnormalities defined on actual values: the abnormality worsened as compared to the abnormality at reference; this also includes the shift from ‘abnormally high’ to ‘abnormally low’ and vice-versa. Post-reference abnormalities are always treatment-emergent with regard to missing abnormalities at reference. The abnormalities ‘abnormally high’ and ‘abnormally low’ are considered equally important.

Abnormalities on changes from reference are always defined as emergent (QTc).

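### SAP 7.2 lists post-challenge urinalysis at Day 12 and Day 28 that the protocol does not schedule, and the SAP 7 denominator counts untested subjects as having no abnormality

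*SAP*

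**What the plan says.** **Timepoints in the SAP.** SAP 7.2 introduces its list with "Blood and urine for laboratory safety assessments will be collected within 56 days of vaccination, pre-vaccination, at 7 days post vaccination" and continues it "prior to challenge on Day -1 or Day -2, post challenge at day 12 and Day 28". Urine is not separated from blood anywhere in that list. SAP Attachment 1 grades urine protein, glucose and blood, and 7.2 takes the worst grade separately for each trial period.

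**Timepoints in the protocol.** Section 9.2.6.2 names blood and urine together only as far as "pre-vaccination, 7 days post-vaccination, and prior to challenge on Day -1 or Day -2". It then adds: "Blood samples will additionally be collected at discharge from the quarantine Unit and at 28 days post-challenge". Section 3.1 describes the same addition: "Blood will additionally be collected for biochemistry and hematology assessments at discharge from the quarantine Unit and at 28 days post-challenge". The Day 28 visit (9.1.6) has "blood samples collected for clinical laboratory tests (hematology and biochemistry only"), and 9.1.5.4 says the same for discharge. The urinalysis row of the Time and Events Schedule is blank at Day 12 and Day 28.

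**Denominators.** The general safety rule in SAP 7 is "Denominator for the percentages is the number of subjects in the considered population and period for a certain regimen". Section 7.2 sets no other rule for laboratory data. The ECG section (7.4) does: "Percentages will be calculated relative to the total number of subjects with data".

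**The concern.** Two faults combine. First, the SAP describes urine data that the protocol does not schedule, and the list of changes in SAP section 2 says nothing about it, so this is not a declared departure. Second, the general denominator makes no distinction between a subject who was tested and found normal and a subject who was never tested.

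Urinalysis is named in the secondary safety endpoint, and safety results are shown by period. Someone who takes SAP 7.2 at face value would believe that urine was examined twice after challenge, and would read an empty or zero line as a clean finding. It would instead be a gap in sampling. The denominator affects any other laboratory test for which some subjects have no sample in a period.

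**Working it through.** The documents state no urinalysis rate, so there is no figure to reproduce. The check compares the schedules, assigns samples to periods, and then computes the percentage each denominator gives.

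**Step 1: schedules side by side (safety laboratory samples).**

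| Timepoint | SAP 7.2 | Protocol 9.2.6.2 and Schedule |
|---|---|---|
| Screening, Day -28, Day -21, Day -2 or -1 | blood and urine | blood and urine |
| Day 12 | blood and urine | blood only |
| Day 28 | blood and urine | blood only |
| Early exit | not listed | urine marked in the Schedule without a condition |

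Protocol 9.1.8 limits all early-exit safety laboratory sampling to exits within 7 days of vaccination. Challenge takes place at least 24 days after vaccination, so under 9.1.8 no post-challenge early exit would give a urinalysis. Under the Schedule it would. The protocol is therefore inconsistent with itself on this sample.

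**Step 2: assignment to periods.** SAP Table 2 starts the Challenge period at the date and time of challenge. The admission urine on Day -2 or -1 falls before it. For a subject who completes the scheduled visits, urinalyses in the Challenge period number 2 according to SAP 7.2 and 0 according to the protocol.

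**Step 3: the percentage.** Rate = x/N, with N = 22 challenged per arm (SAP 1.4).
- Scheduled visits only, all-subjects denominator: 0/22 = 0%, with 0 tested.
- Scheduled visits only, subjects-with-data denominator: 0/0, not estimable.
- One emergent abnormality at early exit or on a repeat test, all-subjects denominator: 1/22 = 4.5%. If enrolment rose to the maximum of 70, all were challenged and the split were even (an assumption), 1/35 = 2.9%.
- The same single result with only that subject tested: 1/1. This is why the number tested must be printed beside the percentage.

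**Step 4: what a zero would mean.** If all 22 were tested and none were abnormal, the two-sided 95% upper bound would be 1 - 0.025^(1/22) = 15.4%. With nobody tested there is no bound. For assumed true rates of 5%, 10% and 20%, the chance of at least one abnormal result among 22 tested subjects is 1 - (1 - p)^22 = 68%, 90% and 99%.

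**Step 5: a second test affected.** Protocol 9.2.6.2 measures cardiac enzymes only on admission and on Days 3, 7 and 11. The post-dose period ends no later than 32 days after vaccination. A subject who withdraws before admission, is never challenged, or is admitted with a later cohort after that limit has no cardiac-enzyme result in it, but still counts in N. For scale, the first cohort vaccinates 26 and challenges 22. If the other 4 had no admission sample in the period (an assumption), 4/26 = 15% of the denominator would be untested, and one abnormality would be reported as 1/26 = 3.8% instead of 1/22 = 4.5%, both arms combined.

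**The case against.** The strongest reply is that this is a slip in a sentence describing sample collection. Safety is descriptive with no formal group comparisons, and both arms share the schedule and the denominator, so no systematic bias between arms follows. No planned analysis contrasts post-dose with post-challenge urinalysis rates. Creatinine, urea and blood urea nitrogen are in the biochemistry panel taken at Day 12 and Day 28. All of this stands, and it limits the weight of the point.

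It is also fair that the SAP 7 denominator is a general rule and that the table layouts are left to the data presentation specifications, which are not available here. But 7.2 offers no alternative, so the general rule applies by default.

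A reader might go further and infer any of the following, which the documents do not support:
- *No urine is taken after challenge.* Urine pregnancy tests are scheduled for women at Day 12 and Day 28. What is missing is urinalysis.
- *The post-challenge rate is forced to be 0%.* The Schedule marks urinalysis at early exit, 9.2.6.2 requires clinically significant worsened results to be repeated, and SAP 7.2 counts every post-baseline measurement in the period. The rate can be above zero.
- *A 0% row will be printed.* Only emerging abnormalities are tabulated, so the row may simply be absent.
- *Vital signs are diluted too.* They are taken daily in quarantine, and no dilution is shown.

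**Conclusion.** The point holds as a mismatch between SAP and protocol together with a denominator that hides missing tests. Protocol 3.1, 9.1.5.4, 9.1.6, 9.2.6.2 and the Schedule agree that Day 12 and Day 28 have no urinalysis; SAP 7.2 says otherwise. On the protocol's schedule, the regular visits give 0/22 per arm with nobody tested, where the correct statement is that the rate cannot be estimated. A single unscheduled abnormality would be reported as 4.5% of a group that was not tested.

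This rests on three assumptions: 22 challenged per arm, sampling as the protocol schedules it, and the SAP 7 denominator carried into the laboratory tables. The consequence is limited to descriptive safety tables. The primary and secondary efficacy results are untouched, and it would be wrong to conclude that renal safety after challenge goes unassessed. The change is worth making before the tables are programmed.

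**What to change.** 1. Reconcile the urine timepoints in SAP 7.2 with protocol 9.2.6.2 and the Time and Events Schedule.
2. Reconcile early-exit urine between the Schedule, which sets no condition, and protocol 9.1.8, which restricts it.
3. In SAP 7.2, define the laboratory denominator as subjects with at least one post-baseline result for that test in that period, on the same principle as SAP 7.4, and print the number tested in each arm.
4. Keep any early-exit or repeat urine results obtained after challenge in the output. Restricting urinalysis tables to the pre-challenge periods would discard valid results that SAP 7.2 says to include.
5. If the reconciled schedule has no urinalysis at Day 12 and Day 28, state that the scheduled visits support no conclusion about urinalysis after challenge.

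The cost is a few sentences in the SAP, one clarification in the protocol for early exit, and one programming rule for the laboratory tables. The fix itself needs no new samples or visits.
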